2.1.2 Exclusion Criteria

2.1.2.1 Patients who are receiving any other investigational agents.

2.1.2.2 Patients who have a history of receiving immune therapy.

2.1.2.3 History of allergic reactions attributed to compounds of similar chemical or biologic composition to nivolumab.

2.1.2.4 History of severe hypersensitivity reaction to any monoclonal antibody.

2.1.2.5 Prior invasive malignancy (except non-melanomatous skin cancer) unless disease free for a minimum of 3 years prior to initiation of study therapy.

2.1.2.6 Patients with active autoimmune disease or history of autoimmune disease that might recur, which may affect vital organ function or require immune suppressive treatment including systemic corticosteroids. These include but are not limited to patients with a history of immune related neurologic disease, multiple sclerosis, autoimmune (demyelinating) neuropathy, Guillain-Barre syndrome or CIDP, myasthenia gravis; systemic autoimmune disease such as SLE, connective tissue diseases, scleroderma, inflammatory bowel disease (IBD), Crohn's, ulcerative colitis, hepatitis ; and patients with a history of toxic epidermal necrolysis (TEN), Stevens-Johnson syndrome, or phospholipid syndrome. Such diseases should be excluded because of the risk of recurrence or exacerbation of disease.

Of note, patients with vitiligo, endocrine deficiencies including thyroiditis managed with replacement hormones including physiologic corticosteroids are eligible. Patients with rheumatoid arthritis and other arthropathies, Sjögren's syndrome and psoriasis controlled with topical medication and patients with positive serology, such as antinuclear antibodies (ANA), anti-thyroid antibodies should be evaluated for the presence of target organ involvement and potential need for systemic treatment but should otherwise be eligible.

2.1.2.7 The patient must not be currently on a corticosteroid dose greater than dexamethasone 1 mg per day or its equivalent.

2.1.2.8 Uncontrolled intercurrent illness including, but not limited to, ongoing or active infection, symptomatic congestive heart failure, unstable angina pectoris, cardiac

arrhythmia, or psychiatric illness/social situations (within timeframes identified in the bullets below) that would limit compliance with study requirements.

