3.3 DOSE MODIFICATIONS

There are no planned dose reductions for nivolumab.

The tables below outline the criteria for delaying (then restarting) or stopping treatment by toxicity type.

Treatment will be discontinued if AE is not resolved for 4 weeks.

Skin Rash and Oral Lesions	Management
Grade 1	Continue treatment. No change in dose *.
Grade 2	Hold* until \leq Grade resolved. Consider steroid treatment $>$ 5-7 days Resume at same dose level.
Grade 3	Hold* until \leq Grade 1. Resume at same level at investigator discretion
Grade 4	Off protocol therapy
*Patients with purpuric or bullous lesions must be evaluated for vasculitis, Steven-Johnson syndrome, TEN, and autoimmune bullous disease including oral lesions of bullous pemphigus/pemphigoid. Pruritus may occur with or without skin rash and should be treated symptomatically if there is no associated liver or GI toxicity. Note skin rash typically occurs early and may be followed by additional events particularly during steroids tapering.	
Recommended management: See AE management guidelines (Appendix C)	

Liver Function AST/ALT/T. Bili *	Management
Grade 1	Continue treatment
Grade 2	Hold until less than or equal to Grade 1. Resume at same dose level. Consider steroid treatment if persists $>$ 5-7 days or worsens.

Liver Function AST/ALT/T. Bili *	Management
Grade 3	Off protocol therapy
Grade 4	Off protocol therapy
Continued treatment of active immune mediated hepatitis may exacerbate ongoing inflammation. Holding drug to evaluate LFT changes and early treatment are recommended. LFT changes may occur during steroid tapers from other events and may occur together with other GI events including cholecystitis/pancreatitis.	
Recommended management: See Hepatic AE management algorithm (Appendix C)	
* Total bilirubin not used for determining AEs in patients with Gilbert syndrome.	

Renal Function Serum Creatinine	Management
Grade 1	Continue treatment.
Grade 2	Hold until \leq Grade 1. Resume at same dose level.
Grade 3	Hold until \leq Grade 1. Resume at same dose level.
Grade 4	Off protocol therapy
For Grade 2 or greater, consider renal biopsy. Corticosteroids may be required for Grade 2/3, high dose for grade 4.	
Recommended management: see Renal AE management algorithm (Appendix C)	

Diarrhea/ Colitis	Management
Grade 1	Diarrhea/asymptomatic colitis, continue treatment at PI discretion.

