Grade 1	Asymptomatic TSH elevation *. Treatment may continue while having endocrine evaluation. endocrine consult is recommended.
Grade 2	Hold until patients are on a stable replacement hormone regimen. If treated with steroids patients must be stable off steroids for two weeks. Resume at same dose level.
Grade 3	Off protocol therapy
Grade 4	Off protocol therapy
Note all patients with symptomatic pituitary enlargement, exclusive of hormone deficiency, but including severe headache or enlarged pituitary with enhancement on MRI should be considered grade 3 events. Isolated thyroid or testosterone deficiency may be treated as grade 2 if there are no other associated deficiencies and adrenal function is monitored.	

Endocrine Hypophysitis Adrenal Insufficiency	Management
	Please evaluate pituitary function before beginning steroid therapy or replacement therapy of any kind. *Note patients with thyroiditis may be retreated on replacement therapy. Patients must be evaluated to rule out pituitary disease prior to initiating thyroid replacement.
	Recommended management: See Endocrine Management Algorithm (Appendix C)

Fever	Management
Grade 1	No change in dose.
Grade 2	Hold until \leq Grade 1. Resume at same dose level.
Grade 3	Hold until \leq Grade 1. Resume at same dose level.
Grade 4	Off protocol therapy
Patients with fever should be evaluated as clinically appropriate. Patients may experience isolated fever during infusion reactions or up to several days after infusion. Evaluation over the course of 1-2 weeks should be done for other autoimmune events that may present as fever.	

ALL OTHER EVENTS: NOT AGENT RELATED OR AGENT RELATED NON-IMMUN RELATED	Management
Grade 1	No change in dose
Grade 2	Can continue treatment at PI discretion.
Grade 3	Hold until \leq Grade 1 continue at investigator discretion with the following exception: Grade 3 lymphopenia or asymptomatic amylase or lipase does not require dose delay

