3.7.1 Criteria for Removal from Protocol Therapy

- Completion of protocol therapy
- Progressive disease (See [Appendix D](#) for treatment discontinuation guidance)
- Participant requests to be withdrawn from active therapy
- Unacceptable Toxicity as defined in Section [3.3](#)
- PI discretion
- Positive pregnancy test
- Patient becomes unable to tolerate an MRI study with intravenous gadolinium contrast.

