Rule out non-inflammatory causes. If non-inflammatory cause, treat accordingly and continue I-O therapy. Consider imaging for obstruction.

[figure not shown]
Patients on IV steroids may be switched to an equivalent dose of oral corticosteroids (e.g. prednisone) at start of tapering or earlier, once sustained clinical improvement is observed. Lower bioavailability of oral corticosteroids should be taken into account when switching to the equivalent dose of oral corticosteroids.

*I-O therapy may be delayed rather than discontinued if AST/ALT \leq 8 x ULN or T.bili \leq 5 x ULN.

**The recommended starting dose for grade 4 hepatitis is 2 mg/kg/day methylprednisolone IV.

Pulmonary Adverse Event Management Algorithm

[figure not shown]
Rule out non-inflammatory causes. If non-inflammatory cause, treat accordingly and continue I-O therapy. Evaluate with imaging and pulmonary consultation.

Patients on IV steroids may be switched to an equivalent dose of oral corticosteroids (e.g. prednisone) at start of tapering or earlier, once sustained clinical improvement is observed. Lower bioavailability of oral corticosteroids should be taken into account when switching to the equivalent dose of oral corticosteroids.

Renal Adverse Event Management Algorithm

[figure not shown]
Rule out non-inflammatory causes. If non-inflammatory cause, treat accordingly and continue I-O therapy

Patients on IV steroids may be switched to an equivalent dose of oral corticosteroids (e.g. prednisone) at start of tapering or earlier, once sustained clinical improvement is observed. Lower bioavailability of oral corticosteroids should be taken into account when switching to the equivalent dose of oral corticosteroids.

Skin Adverse Event Management Algorithm

Rule out non-inflammatory causes. If non-inflammatory cause, treat accordingly and continue I-O therapy.

Patients on IV steroids may be switched to an equivalent dose of oral corticosteroids (e.g. prednisone) at start of tapering or earlier, once sustained clinical improvement is observed. Lower bioavailability of oral corticosteroids should be taken into account when switching to the equivalent dose of oral corticosteroids.

*Refer to NCI CTCAE v4 for term-specific grading criteria.

^If SJS/TEN is suspected, withhold I-O therapy and refer patient for specialized care for assessment and treatment. If SJS or TEN is diagnosed, permanently discontinue I-O therapy.

[figure not shown]

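### The Section 3.3 skin table and the Appendix C skin footnote differ on treatment after Stevens-Johnson syndrome/TEN, and nothing says which governs

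*Combined protocol and SAP*

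**What the plan says.** Section 3.3 introduces its tables as operative rules: "The tables below outline the criteria for delaying (then restarting) or stopping treatment by toxicity type". In the table for skin rash and oral lesions, Grade 1 continues without dose change. Grade 2 is held and then resumed at the same dose level. Grade 3 is held until Grade 1 or lower and then "Resume at same level at investigator discretion". Grade 4 is off protocol therapy. Grades 1 to 3 carry an asterisk leading to a footnote: "Patients with purpuric or bullous lesions must be evaluated for vasculitis, Steven-Johnson syndrome, TEN" (the list goes on to autoimmune bullous disease). The footnote does not say what follows if SJS or TEN is suspected or confirmed. The table closes by pointing to Appendix C under the label of recommended management.

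The skin algorithm in Appendix C (Section 16.3) has its own footnote. If SJS/TEN is suspected, treatment is withheld and the patient referred. It then says: "If SJS or TEN is diagnosed, permanently discontinue I-O therapy". The footnote names no grade.

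Section 3.7.1 lists, among the reasons for removal from therapy, "Unacceptable Toxicity as defined in Section" 3.3. It does not name Appendix C for toxicity.

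**The concern.** The two passages answer the same question, whether a patient with suspected or diagnosed SJS/TEN receives more nivolumab, by different criteria. The table uses grade and the appendix uses diagnosis. An investigator working from the table can reach a different action from one working from the appendix, and each can point to protocol text in support. At stake are re-exposure to the study drug after such a reaction and the ability of a monitor to say whether a given decision was a deviation.

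**Working it through.** No arithmetic applies, and the plan states no figure on this point. The check sets the passages side by side.

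| Situation | Section 3.3 skin table | Appendix C skin footnote | Can both be followed? |
|---|---|---|---|
| Suspected, Grade 1 | Continue; evaluate purpuric or bullous lesions | Withhold and refer | No |
| Suspected, Grade 2 or 3 | Hold | Withhold and refer | Yes |
| Diagnosed, Grade 1 | Continue | Stop permanently | No |
| Diagnosed, Grade 2 | Hold, then resume at the same dose level | Stop permanently | No |
| Diagnosed, Grade 3 | Hold, then may resume at discretion | Stop permanently | Only if the discretion is never used |
| Suspected or diagnosed, Grade 4 | Off protocol therapy | Withhold, or stop permanently | Yes |

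Section 3.3 also discontinues treatment for any event unresolved for 4 weeks. That narrows the Grade 2 and Grade 3 rows to events that settle in time; it does not remove them.

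**Which rows can occur.** Sections 6.4 and 8.1.4 grade by CTCAE version 5.0, while the Appendix C skin algorithm cites version 4. Neither is reproduced, so the documents do not show whether SJS/TEN could be graded 1 or 2. If it is never graded below 3, what remains is the Grade 3 row, where the table permits what the appendix forbids. If lower grades are possible, the direct conflicts at Grades 1 and 2 apply as well.

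**Does any passage rank the two sources?** None was found.
- Section 3.3 calls Appendix C recommended, and Section 3.7.1 ties removal for toxicity to Section 3.3. Both suggest that the table governs.
- Section 4.1 makes Appendix C binding in one setting, antidiarrheal treatment, where it demands strict adherence. No such statement is made for skin events.
- A rule that the stricter text wins, or that Appendix C wins, cannot be inferred. For liver events the direction is reversed: Section 3.3 takes Grade 3 off therapy, while an Appendix C footnote allows delay instead of discontinuation within stated laboratory limits. The flow chart is not shown, so this serves only as evidence that precedence needs stating.

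**Is this simply how Section 3.3 is written?** No. The neurologic table has a footnote naming diagnoses that end treatment. The skin footnote names SJS and TEN and stops at evaluation.

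**The case against.** The strongest reply is that Section 3.3 already leads to the right page. Evaluation for SJS/TEN is mandatory, and the same table sends the reader to Appendix C, where the action is stated. The Grade 3 row is permissive, so an investigator satisfies both passages by not resuming. Section 3.7.1 also lists investigator discretion as a separate reason for removal, so nothing blocks a stop under Appendix C.

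Much of this stands. A reader might infer that Section 3.3 lets treatment go on by grade alone. The documents do not support that: the evaluation footnote, the cross-reference, the discretion at Grade 3, the stop at Grade 4 and the 4-week limit all qualify the grade rows.

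The reply does not dispose of the point. Compatibility by not resuming covers only the Grade 3 row; Grade 1 continues and Grade 2 resumes with no such discretion in the text. That stopping is allowed does not settle whether it is required. The cross-reference leads to a rule labelled as recommended.

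A further fair caution is that the Appendix C skin flow chart is not shown, so where its footnote attaches cannot be checked. The footnote's wording is legible and depends on suspicion or diagnosis, not grade.

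**Conclusion.** The inconsistency is real and confined to SJS/TEN. It rests on the footnote applying as worded, at least at Grade 3, and on no ranking of the two sources elsewhere. Its smallest form is the Grade 3 mismatch; its largest adds direct conflicts at Grades 1 and 2, if such events can carry those grades. The documents give no incidence, so the number of patients affected cannot be sized. Sample size, type I error and power do not depend on it.

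Three stronger readings are not supported.
- A reader might infer that the entry criteria contradict Section 3.3, since 2.1.2.6 excludes "patients with a history of toxic epidermal necrolysis (TEN), Stevens-Johnson syndrome". That criterion governs history at entry and sets no rule for events on treatment. The conflict rests on Appendix C.
- A reader might infer the same contradiction for severe hypersensitivity, because 2.1.2.4 excludes "History of severe hypersensitivity reaction to any monoclonal antibody" while the Grade 3 row for other non-immune events says to hold until Grade 1 or lower and "continue at investigator discretion with the following exception". Section 3.3 has no dedicated table for such reactions, but its generic tables cover them, and no on-treatment passage says otherwise.
- A reader might infer that a planned analysis of toxicity discontinuations would be distorted. Section 10.3.3 plans only frequency tables of adverse event type and grade.

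**What to change.** Reconcile the skin rows and footnote of Section 3.3 with the SJS/TEN footnote of Appendix C, so that both state the same action for a suspected case and the same action for a diagnosed case. In Section 3.3 or 3.7.1, state which source governs where the tables and Appendix C differ. Which rule is right is for the sponsor's clinicians; this review takes no position.

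The cost is a wording amendment, with the IRB review that the Statement of Compliance requires for any amendment. No data collection, analysis or sample size changes.

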Grade 2	Hold until \leq Grade 1 or baseline. Consider steroid treatment if persists $> 5-7$ days.
Grade 3	Off protocol therapy.
Grade 4	Off protocol therapy.
Patients with grade 2 symptoms but normal colonoscopy and biopsies may be retreated after resolution.	
Patients with grade 2 persistent symptoms greater than 14 days who require steroids should be taken off study treatment.	
Please evaluate pituitary function prior to starting steroids if possible without compromising acute care.	
Evaluation for all patients for additional causes includes C. diff , acute and self-limited infectious and foodborne illness, ischemic bowel, diverticulitis, and IBD.	
Recommended management: see GI AE management Algorithm (Appendix C).	

Pancreatitis Amylase/Lipase	Management
Grade 1	Continue treatment if asymptomatic.
Grade 2	Hold until \leq Grade 1. Resume at same dose level if asymptomatic. Asymptomatic Grade 2 is defined as elevation of both amylase and lipase.

Pancreatitis Amylase/Lipase	Management
Grade 3	Off protocol therapy
Grade 4	Off protocol therapy

Patients may develop symptomatic and radiologic evidence of pancreatitis as well as DM and DKA. Lipase and/or amylase elevation may occur during the period of steroid withdrawal and with other immune mediated events or associated with colitis, hepatitis, and patients who have asymptomatic lipase and/or amylase elevation typically have self-limited course and may be retreated.
 
For treatment management of symptomatic pancreatitis please follow the Hepatic Adverse Event Management Algorithm (Appendix C).
	

Pneumonitis	Management
Grade 1	Hold dose pending evaluation and resolution to baseline including baseline pO ₂ . Resume; no change in dose after pulmonary and/or ID consultation
Grade 2	Hold dose pending evaluation and resolution to baseline including baseline pO ₂ . Resume; no change in dose after pulmonary and/or ID consultation if lymphocytic pneumonitis is excluded. Off study if grade 2 symptoms do not improve or worsen after 2 weeks of steroids and dose delay.
Grade 3	Off protocol therapy.
Grade 4	Off protocol therapy.

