Grade 4	Off protocol therapy, with the following exceptions: 
Grade 4 neutropenia \leq 7 daysGrade 4 lymphopenia or leukopenia or asymptomatic amylase or lipaseIsolated Grade 4 electrolyte imbalances/abnormalities that are not associated with clinical sequelae and are corrected with supplementation/appropriate management within 72 hours of their onsetGrade 4 drug-related endocrinopathy adverse events, such as, hyper- or hypothyroidism, or glucose intolerance, which resolve or are adequately controlled with physiologic hormone replacement (corticosteroids, thyroid hormones) or glucose-controlling agents,

ALL OTHER EVENTS: NOT AGENT RELATED OR AGENT RELATED NON-IMMUN RELATED	Management
	respectively, may not require discontinuation after discussion with and approval from the BMS Medical Monitor.
Recommended management: As clinically indicated	

ALL OTHER EVENTS: IMMUNE RELATED	Management
Grade 1	No change in dose
Grade 2	Hold until \leq Grade 1 OR baseline. When resolved or following steroids, resume at same dose level. 
Exception: Nivolumab should be discontinued for any grade 2 drug-related uveitis, eye pain or blurred vision that does not respond to topical therapy and does not improve to Grade 1 severity within the re-treatment period OR requires systemic treatment
Grade 3	
Any grade 3 or 4 drug-related laboratory abnormality or electrolyte abnormality, not associated with underlying organ pathology, that does not require treatment except for electrolyte replacement OR hormone/steroid replacement does not require treatment discontinuation.Any grade 2 or 3 drug-related uveitis or eye pain or blurred vision that does not respond to topical therapy and does not improve to Grade 1 severity within the re-treatment period OR requires systemic treatment requires treatment discontinuation

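### Section 3.3 both stops and exempts asymptomatic Grade 3-4 amylase/lipase elevation, with no rule on which table governs

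*Combined protocol and SAP*

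**What the plan says.** Section 3.3 sets the rules for delaying or stopping nivolumab in a series of tables, one per type of toxicity. Four places bear on amylase and lipase.

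- **Pancreatitis Amylase/Lipase table.** Grade 1 continues if there are no symptoms. Grade 2 is held until Grade 1 or lower, then "Resume at same dose level if asymptomatic". The Grade 3 and Grade 4 rows each read "Off protocol therapy", with no exception. The note below the rows adds that "patients who have asymptomatic lipase and/or amylase elevation typically have self-limited course and may be retreated", and it names no grade.
- **All other events, not agent related or agent related but non-immune.** Grade 2: "Can continue treatment at PI discretion". Grade 3 is held, except that "Grade 3 lymphopenia or asymptomatic amylase or lipase does not require dose delay". Grade 4 goes off therapy, but asymptomatic amylase or lipase is a listed exception.
- **All other events, immune related.** The Grade 3 row does not name the enzymes. It has a general clause whose subject is "Any grade 3 or 4 drug-related laboratory abnormality or electrolyte abnormality". After limiting this to cases without underlying organ disease, the clause ends "that does not require treatment except for electrolyte replacement OR hormone/steroid replacement does not require treatment discontinuation". The Grade 4 row repeats the listed exception for asymptomatic amylase or lipase.
- **General rule ahead of the tables.** "Treatment will be discontinued if AE is not resolved for 4 weeks".

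On the number of doses, the Precis and Section 3.1 give a limit of 20 treatments in 16 cycles or 64 weeks. The Precis, Section 3.1 and Study Calendar footnote 2 agree on the schedule: two-weekly dosing in cycles 1-2, then four-weekly dosing in cycles 3-16.

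**The concern.** Section 3.7.1 makes unacceptable toxicity, as Section 3.3 defines it, a criterion for removal from protocol therapy. The conflict therefore sits inside a binding stopping rule. Amylase and lipase belong to the biochemical profile scheduled for day 1 of every cycle (Study Calendar, footnote 5), so elevations without symptoms will be looked for routinely.

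Two patients with the same asymptomatic Grade 3 value could be handled in opposite ways, one stopped for good and the other dosed without delay. Section 8.8 counts any non-compliance with the protocol as a deviation, and whichever line an investigator follows, another line in Section 3.3 points the other way. At stake are consistent handling, unnecessary loss of treatment, and continued dosing where stopping may have been meant.

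**Working it through.** **Step 1. Set the rules side by side for an asymptomatic elevation.**

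| Grade | Pancreatitis Amylase/Lipase | All other events, non-immune | All other events, immune related |
|---|---|---|---|
| 2 | Hold, then resume | May continue at investigator's choice | Hold, then resume |
| 3 | Off | No delay (named) | Not named; general laboratory clause exempts from discontinuation but gives no hold or continue action |
| 4 | Off | Exempt from off (named) | Exempt from off (named) |

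For stopping: 2 rows. Against stopping: 1 named exception at Grade 3 + 2 at Grade 4 = 3 named exceptions, plus 1 note and 1 general clause.

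**Step 2. Does the Pancreatitis table cover only clinical pancreatitis?** Not as written. Its heading names the enzymes, its Grade 1 row turns on the absence of symptoms, and its Grade 2 row defines an asymptomatic case. Nothing narrows the scope at Grades 3 and 4.

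**Step 3. Does the dedicated table override the All other events tables?** The word other suggests so, but no text says it. On that reading all three named exceptions have no effect, since every amylase or lipase value would already belong to the dedicated table. The retreatment note would then have to mean Grade 2 or lower, a limit it does not state.

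**Step 4. Do the tables divide by cause?** Suppose the Pancreatitis table governs immune-related elevation and the non-immune table governs the rest. The two non-immune exceptions then keep their effect, and the Grade 2 difference follows cause. At immune-related Grade 4, however, one row still says off while another names the same finding as exempt. The general laboratory clause also remains in tension with the off rows.

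**Step 5. Do all the rules work together?** No. Asymptomatic Grade 2 is held under the Pancreatitis table, while the more severe Grade 3 needs no delay under the non-immune table.

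**Step 6. Dose count (editorial).** The stated figure is 20. From the schedule:

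- Infusions: 2 cycles x 2 + 14 cycles x 1 = 4 + 14 = 18.
- Duration: 16 cycles x 4 weeks = 64 weeks, as stated.

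With two-weekly dosing in cycles 1 to k, the total is 2k + (16 - k) = 16 + k. This gives 18 at k = 2 and reaches 20 only at k = 4. Keeping k = 2, 20 infusions would need 2 + (20 - 4) = 18 cycles, or 18 x 4 = 72 weeks. Neither variant matches the text, so the figure of 20 is not reproduced.

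**The case against.** The strongest reply is that a sensible investigator can find the intended rule. The note, the three named exceptions and the general laboratory clause all favour not stopping for asymptomatic values. The two off rows do not mention asymptomatic patients, and a specific exception is commonly read as qualifying a general row. This stands as evidence of intent, and it decides which fix to recommend. It does not make the rule workable as written, because the same table deals with asymptomatic cases at Grades 1 and 2 and then drops the distinction.

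The division by cause is also a fair reading. The Pancreatitis note does speak of immune-mediated events, and the division removes part of the conflict. The protocol does not state it, though, and it fails at immune-related Grade 4.

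Investigator discretion does not settle the matter. Section 3.7.1 lists it as a reason to remove a patient, not as authority to override a mandatory stop.

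The practical consequence is modest. Section 7.4.1 has the team discuss each patient weekly and the principal investigator review each patient's adverse event data, which reduces inconsistent handling. Under Study Calendar footnote 7, patients who stop within the first year and have not progressed by the 28-day visit continue MRI every 8 weeks until progression or 1 year from the start of treatment. Assessment for PFS6 therefore continues.

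**Conclusion.** The contradiction is real, and Section 3.3 cannot be followed as written for asymptomatic Grade 3-4 amylase or lipase elevation. It should be corrected because it governs removal from therapy. It is a clarity and patient-handling problem, not a flaw in the statistical design. The conclusion rests only on the wording of Section 3.3 and the absence of any precedence rule.

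A reader might infer more than the documents support in four respects:

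- **That the strict and lenient rules are equally likely to have been meant.** Most of the text favours the lenient one.
- **That the 4-week rule plainly limits continued dosing.** That rule speaks of an AE. Section 6.1 records a laboratory value as an AE only under listed conditions, which an untreated, asymptomatic elevation may not meet. Section 6.1 concerns recording, not dosing, so the question is open. Applying the 4-week rule could also undo the exception from dose delay.
- **That the number of scheduled enzyme tests measures the problem.** It counts opportunities for detection. The documents give no rate of Grade 3-4 elevation.
- **That the dose limit must be 18.** This is the natural correction, since the cycles 1-2 and 3-16 schedule is repeated consistently and fits 64 weeks. The documents cannot wholly exclude that two-weekly dosing through cycle 4 was intended. The 16-cycle limit binds first, so the discrepancy does not change PFS6, the sample size or the conclusions.

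**What to change.** Recommended, subject to the clinical team's confirmation:

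1. Limit the Grade 3 and Grade 4 stopping rows of the Pancreatitis Amylase/Lipase table to symptomatic or radiologic pancreatitis.
2. State one hold or continue action for asymptomatic elevation at each of Grades 2, 3 and 4, and say that it applies whatever the cause (or give the action by cause explicitly). This also settles the Grade 2 difference and supplies the missing action for immune-related Grade 3.
3. Decide, and write down, whether the 4-week non-resolution rule covers asymptomatic enzyme values.

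If the team instead intends the strict rule, it should delete amylase and lipase from the three named exceptions, exclude them from the general laboratory clause, and limit the retreatment note to Grade 2 or lower.

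Editorial: change 20 to 18 treatments in the Precis and Section 3.1, or confirm the schedule if 20 was meant.

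Cost: a short wording amendment, with a clinical decision behind it because a stopping rule is being settled, and IRB approval before use. If the schedule stands, the regimen does not change. Sample size and analysis are unchanged.
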